### **3.2 Proposed Primary and Secondary Outcome Measures**

#### 3.2.1 Primary Outcomes

The primary outcome is any unplanned secondary procedure within 2 years of the initial joint replacement surgery. A Central Adjudication Committee will review each reported secondary procedure to determine that they are study events (i.e. unplanned) and they will confirm the type of the procedure and the reason for the procedure (**Table 1**).

Specific unplanned secondary procedures include:

1. Closed reduction of hip dislocation
2. Open reduction of hip dislocation
3. Open reduction of fracture
4. Soft tissue procedure
5. Insertion of antibiotic spacer
6. Full implant exchange
7. Partial implant exchange – stem only
8. Partial implant exchange - head only
9. Partial implant exchange - liner only
10. Partial implant exchange - head and liner
11. Partial implant exchange – acetabular component only
12. Partial implant exchange – acetabular component and head
13. Implant adjustment – re-orientation of the stem
14. Implant adjustment – re-orientation of the acetabulum component
15. Implant removal with no replacement
16. Excision heterotopic ossification
17. Supplementary fixation

Classification of the reason for secondary procedures is as follows:

1. Treat a peri-prosthetic fracture
2. Treat hip instability or dislocation
3. Treat infection – superficial
4. Treat infection – deep
5. Treat wound necrosis
6. Treat another wound healing problem

7. Remove heterotopic ossification
8. Manage abductor failure
9. Manage another soft tissue problem (i.e. pseudotumor)
10. Correct implant failure –loosening or subsidence
11. Correct implant failure - breakage
12. Treat implant wear
13. Treat osteolysis
14. Treat implant corrosion
15. Improve function
16. Relieve pain

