Based upon aggregate data from the pilot study, annual mortality rates of 15% and a loss to follow-up of 5% in each group were assumed, these rates applying to each of the two years of follow-up. Informed by the meta-analysis, the following assumptions were made: a one year risk of having a secondary procedure of 5% in the HA group and a risk of 1% in the second year. Various values of the relative risk reduction (HA vs. THA) were then used to identify the specific value that would correspond to a cumulative risk difference between THA and HA of 5% after 2 years. This figure was identified in a survey of participating surgeons as the minimally important difference to clinicians. Annual event risks by group were converted into equivalent hazard rates, assuming for simplicity that the hazard rate would be approximately constant within each of the two years. It is estimated that approximately 72% of the group receiving THA and 76% of the group receiving HA will be event-free and available for further follow-up at the start of the second year. The sample size was increased to allow for a combined 7.6% crossover rate from the assigned to the alternate treatment, based on pilot data. These assumptions lead to a required total sample size of 1,316 patients, which will yield an expected number of 96 secondary procedures. The associated relative risk reduction (RRR) is 0.45.

These calculations were repeated after replacing the 5% event risk at one year for HA by 4% and 6% and leaving the other factors unchanged (**Table 3b**). To account for potential surgeon level effects, the sample size has been further increased by 9% to 1,434.

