10 weeks (8-12 weeks window)	In Person/ Hospital/Clinic (if prior to D/C) or Telephone	•Follow-up Form, and TUG Test •SP, AE Forms •SF-12, WOMAC, EQ-5D (self-administered*) •Radiographs
	↓	
6 months (5-7 months window)	In Person/ Hospital/Clinic or Telephone	•Follow-up Form, and TUG Test •SP, AE Forms •SF-12, WOMAC, EQ-5D (self-administered*)
	↓	
9 months (8-10 months window)	Telephone or In Person/ Hospital/Clinic	•Follow-up Form •SP, AE Forms •SF-12, WOMAC, EQ-5D (interview-administered)
	↓	
12 months (11-13 months window)	In Person/ Hospital/Clinic or Telephone	•Follow-up Form, and TUG Test •SP, AE Forms •SF-12, WOMAC, EQ-5D (self-administered*) •Radiographs
	↓	
18 months (17-19 months window)	Telephone or In Person/ Hospital/Clinic	•Follow-up Form •SP, AE Forms •SF-12, WOMAC, EQ-5D (interview-administered)
	↓	
24 months (>24 months window)	In Person/ Hospital/Clinic or Telephone	•Follow-up Form, and TUG Test •SP, AE Forms •SF-12, WOMAC, EQ-5D (self-administered*) •Radiographs •Planned RS after 24 months

\* Prepare for interview-administered data collection if patient unable to complete self-administered forms.

AE = Adverse Event, D/C = Discharge, EQ-5D = EuroQol-5D, SP = Secondary Procedures, SF-12 = Short Form-12, TUG = Timed Up and Go, WOMAC = Western Ontario McMaster Osteoarthritis Index.

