2.5 Follow-up Processes

| Time-point | Assessment Procedures | Data Collection |
|-------------------------|---|---|
| 1 week (Up to 3 months) | In Person/Hospital/Clinic (if prior to discharge) | •Follow-up Form •Secondary Procedures, AE Forms •SF-12, WOMAC, EQ-5D (self-administered*) (asking about patient function prior to surgery) |

| | | |
|-----------------------------------|---|---|
| 1 week (Up to 5 weeks) | In Person/Hospital/Clinic (if prior to discharge) | •TUG Test |
| 10 weeks (5 weeks to 4 months) | In Person/Hospital/Clinic (if prior to discharge) or Telephone | •Follow-up Form and TUG Test •Secondary Procedures, AE Forms •SF-12, WOMAC, EQ-5D (self-administered*) •Radiographs |
| 6 months (4 to 7.5 months) | In Person/Hospital/Clinic or Telephone | •Follow-up Form and TUG Test •Secondary Procedures, AE Forms •SF-12, WOMAC, EQ-5D (self-administered*) |
| 9 months (7.5 to 10.5 months) | In Person/Hospital/Clinic or Telephone | •Follow-up Form •Secondary Procedures, AE Forms •SF-12, WOMAC, EQ-5D (interview-administered) |
| 12 months (10.5 to 15 months) | In Person/Hospital/Clinic or Telephone | •Follow-up Form and TUG Test •Secondary Procedures, AE Forms •SF-12, WOMAC, EQ-5D (self-administered*) •Radiographs |
| 18 months (15 to 21 months) | In Person/Hospital/Clinic or Telephone | •Follow-up Form •Secondary Procedures, AE Forms •SF-12, WOMAC, EQ-5D (interview-administered) |
| 24 months (21 to 30 months) | In Person/Hospital/Clinic or Telephone | •Follow-up Form and TUG Test •Secondary Procedures, AE Forms •SF-12, WOMAC, EQ-5D (self-administered*) •Radiographs •Planned revision surgery after 24 months |

* Interview-administered data collection done if patient was unable to complete self-administered forms.
 AE = Adverse Event, EQ-5D = EuroQol-5D, SF-12 = Short Form-12, TUG = Timed Up and Go, WOMAC = Western Ontario McMaster Osteoarthritis Index.

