2.6 Outcome Definitions

Primary Outcome

| Outcome | Definition |
|---|---|
| Unplanned Secondary Hip Procedure (study event) | Unplanned secondary procedures that were classified as study events included: 
 ○ Closed reduction of hip dislocation ○ Open reduction of hip dislocation ○ Open reduction of fracture ○ Soft tissue procedure ○ Insertion of antibiotic spacer ○ Full implant exchange ○ Partial implant exchange – stem only ○ Partial implant exchange - head only ○ Partial implant exchange - liner only |

| Outcome | Definition |
|--|---|
| | 
 ○ Partial implant exchange - head and liner ○ Partial implant exchange – acetabular component only ○ Partial implant exchange – acetabular component and head ○ Implant adjustment – re-orientation of the stem ○ Implant adjustment – re-orientation of the acetabulum component ○ Implant removal with no replacement ○ Excision heterotopic ossification ○ Supplementary fixation ○ Other |
| Reason for Unplanned Secondary Procedure | 
Classification of the reason for unplanned secondary procedures included:
 
 ○ Treat a peri-prosthetic fracture ○ Treat hip instability or dislocation ○ Treat infection – superficial ○ Treat infection – deep ○ Treat wound necrosis ○ Treat another wound healing problem ○ Remove heterotopic ossification ○ Manage abductor failure ○ Manage another soft tissue problem (i.e. pseudotumor) ○ Correct implant failure –loosening or subsidence ○ Correct implant failure - breakage ○ Treat implant wear ○ Treat osteolysis ○ Treat implant corrosion ○ Improve function ○ Relieve pain |

Secondary Outcomes

| Outcome | Definition |
|--------------------------|---|
| Mortality | Mortality was adjudicated by the Central Adjudication Committee and it was considered to be an event if it occurred within 24-months of the initial hip fracture surgery. |
| Serious Adverse Events | Serious adverse events, as diagnosed by physicians at the clinical sites, were documented. A serious adverse event was defined as any adverse event that is fatal, life threatening, requires or prolongs hospital stay, results in persistent or significant disability or incapacity, a congenital anomaly or birth defect, or an important medical event, symptom, sign, illness, or experience that develops or worsens in severity during the study. |

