
2.7 Overview of Adjudication

Adjudication Processes

The following information was excerpted from the HEALTH Adjudication Charter, which documents the responsibilities of the Central Adjudication Committee and the adjudication processes for the HEALTH trial.

1) Fracture Eligibility

The Central Adjudication Committee adjudicated fracture eligibility for all patients based on available pre-surgery and post-surgery x-rays, and completed case report forms. If the fracture did not meet all inclusion criteria or met one of the exclusion criteria, the fracture was deemed ineligible.

2) Technical Placement of Prostheses

The Central Adjudication Committee adjudicated the technical placement of the prosthesis based on available pre-surgery and post-surgery x-rays to determine if the quality of the implant placement was acceptable or unacceptable. This was unrelated to fracture eligibility.

3) Additional Surgical Procedures

The Central Adjudication Committee adjudicated additional surgical procedures that occurred within two years of initial surgery after the participant had completed their 24-month visit (or following early withdrawal) to determine if they were study events. Planned surgeries were not considered study events. If a participant had multiple unplanned surgeries for one indication, each unplanned surgery was considered a study event in addition to the first. Any unplanned surgery after the initial fixation that satisfied the criteria below was considered to be a study event:

- Treat a peri-prosthetic fracture
- Treat hip instability or dislocation
- Treat infection – superficial
- Treat infection – deep
- Treat another wound healing problem
- Treat another soft tissue problem
- Remove heterotopic ossification
- Manage abductor failure
- Correct implant failure – loosening or subsidence
- Correct implant failure – breakage
- Treat implant wear and corrosion
- Treat osteolysis
- Treat neurovascular injury
- Improve function
- Relieve pain

The Central Adjudication Committee reviewed all available x-rays, and data from the patient's completed case report forms.

4) Hip-Related Complications

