2.8 Statistical Analyses for Primary and Secondary Outcomes

Analyses included patients in the groups to which they were assigned. Patients were censored at 24 months of follow-up or at the time of their last follow-up for patients lost to follow-up. The primary analysis was a proportional hazards model using a competing risk analysis (death as the competing risk) with time to the HEALTH primary study endpoint as the outcome. The independent variable was THA versus HA, and the following covariates were used: age (50-80 years or >80 years), pre-fracture living setting (institutionalized or not institutionalized), pre-fracture functional status (using aid or independent ambulator), and ASA Class (Class I/II or III/IV/V). For these covariates, we used values that were entered into the minimization system at time of enrollment. For our competing risk analyses, we used the method described by Zhou et al. to account for clustering within surgeons.⁶ The estimates from the competing risk analysis for clustered data analyses were marginal estimates. We report the treatment effects as hazard ratios (HRs) with 95% confidence intervals (CIs). No adjustment for multiplicity was made and the 95% CIs do not adjust for multiplicity. Kaplan-Meier curves were constructed for the primary outcome.

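### SAP 2.5 accepts the 24-month visit from month 21, and SAP 2.8 has no clear censoring date for patients seen before month 24; read literally, up to three months without scheduled contact count as event-free

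*SAP*

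**What the plan says.** **Visit window.** SAP 2.5 gives the closing visit as "24 months (21 to 30 months". The same row lists the follow-up, secondary procedures and adverse event forms, so the window covers event ascertainment as well as the questionnaires. Every protocol statement opens the visit no earlier than month 24: Figure 7 has "24 months (>24 months window", and section 6.3 and Appendix 1 have at least 24 months.

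**Outcome horizon.** Protocol 3.2.1 defines the primary outcome as "any unplanned secondary procedure within 2 years of the initial joint replacement surgery". For mortality, SAP 2.6 says that "it was considered to be an event if it occurred within 24-months of the initial hip fracture surgery". Neither horizon was shortened when the window opened earlier.

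**Censoring.** SAP 2.8: "Patients were censored at 24 months of follow-up or at the time of their last follow-up for patients lost to follow-up".

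**Adjudication.** SAP 2.7 has additional procedures reviewed "after the participant had completed their 24-month visit (or following early withdrawal) to determine if they were study events". A patient seen in month 21 or 22 has completed that visit under SAP 2.5.

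**The concern.** Put together, these rules leave a class of patients without a clear censoring date. Someone whose closing visit is at 21.5 months has completed the 24-month visit, has no later scheduled contact in SAP 2.5 or Appendix 1, and would not ordinarily be called lost to follow-up. SAP 2.8 gives only two dates. The last-follow-up date is tied to loss to follow-up, so the literal rule assigns this patient month 24. The final 2.5 months then enter as event-free time that no scheduled contact covered.

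Three things are at stake. Two-year risks of secondary procedure, complication and death would be understated. Mortality is the most exposed, because deaths continue at a steady rate through year 2 while planned procedure rates fall sharply. The affected time also lies in year 2, where SAP 2.11 reports a hazard ratio of 0.24 (95% CI 0.08-0.73) after 1 year and builds part of its interpretation on it. None of the analyses in SAP 2.10 clearly tests the gap: analysis (e) varies the event risk only for patients lost to follow-up, and early completers may fall outside that group.

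**Working it through.** **Inputs (Protocol 7.1).** The planned risks are "a one year risk of having a secondary procedure of 5% in the HA group and a risk of 1% in the second year". Annual mortality is 15% and annual loss to follow-up 5% in each arm. The relative risk reduction is 0.45, so the THA hazard is the HA hazard divided by 0.55. Stated size: 1,316 patients and 96 events, raised to 1,434 patients. Allocation is taken as 1:1.

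**Model.** Hazards are constant within each year, as the protocol assumes.
- HA procedure hazard: -ln(0.95) = 0.05129 in year 1; -ln(0.99) = 0.01005 in year 2.
- THA procedure hazard: 0.09326 and 0.01827.
- Exit hazard: -ln(0.85) - ln(0.95) = 0.16252 + 0.05129 = 0.21381.
- Events in a year that starts with n at risk: n × h/t × (1 - e^(-t)), where h is the procedure hazard and t = h + 0.21381.

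**Reproducing the plan (N = 1,316, 658 per arm).** HA 29.65 + 4.55; THA 52.84 + 7.89; total 94.9. With the risk reduction applied to annual risks instead of hazards, the total is 96.0. The plan states 96. The shares event-free and available at the start of year 2 are 76.7% (HA) and 73.6% (THA), against 76% and 72% stated. The model is close enough to use.

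**Full size (N = 1,434, 717 per arm).** HA 32.31 + 4.95; THA 57.58 + 8.60; total 103.4, of which 13.55 fall in year 2. Person-years: 2,211. Deaths before a first procedure: 2,211 × 0.16252 = 359.

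**Months 21-24.**
- At risk at month 21: HA 550 × e^(-0.75 × 0.22386) = 465; THA 527 × e^(-0.75 × 0.23208) = 443.
- Time credited to month 24: (465 + 443) × 0.25 = 227 person-years.
- Procedures: 465 × 0.01005 × 0.2431 + 443 × 0.01827 × 0.2429 = 1.14 + 1.97 = 3.1, or 3.0% of 103.4 and 3.1/13.55 = 23% of year-2 procedures.
- Deaths: 0.16252 × (465 × 0.2431 + 443 × 0.2429) = 36, or 10% of 359.

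The factors 0.2431 and 0.2429 are (1 - e^(-0.25t))/t.

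**By share of closing visits at month 21.** The documents do not give this share, so the values are assumptions. Power is from the Schoenfeld formula at a hazard ratio of 0.55, two-sided 0.05. With no gap it is 86.0%.

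| Share seen at month 21 | Procedures missed | Deaths missed | Power |
|---|---|---|---|
| 10% | 0.3 | 4 | 85.9% |
| 25% | 0.8 | 9 | 85.7% |
| 50% | 1.6 | 18 | 85.5% |
| 100% (upper bound) | 3.1 | 36 | 84.9% |

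Every row assumes that nothing is reported after the early visit.

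**How sparse the late comparison is.** From the interval in SAP 2.11, SE(log HR) = ln(0.73/0.08)/3.92 = 0.564, so 1/a + 1/b = 0.318. About 19 events, for example 4 against 15, meet this (1/4 + 1/15 = 0.317). The back-calculation ignores covariates and clustering by surgeon.

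**The case against.** **The censoring rule may be a cap.** A patient last seen at 21.5 months has not had 24 months of follow-up, so SAP 2.8 can be read as censoring that patient at the visit. On that reading there is no false event-free time, only shorter follow-up. Neither document defines loss to follow-up. This stands: a reader might infer that three unobserved months were in fact credited, but the documents show only that the literal wording does so and that no rule excludes it.

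**The windows may be bins.** From 10 weeks on, the SAP 2.5 windows run without gaps, which suits assigning collected forms to visits. The SAP does not say that the site schedule changed. This is plausible, but the event forms share the row, so the question of the censoring date remains.

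**Events also arrive outside visits.** Protocol 9.2 and 9.2.1 require prompt reporting of serious adverse events, including deaths and hospital stays, and SAP 2.7 adjudicates procedures up to two years. Some later events would be captured, so the figures above are upper bounds for each assumed share. Passive reporting after a closing visit is still not the same as asking the patient or checking the record.

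**The hazard ratio need not move.** The window is the same in both arms. If missed late events split as the observed ones did, the ratio is unchanged. A reader might infer that the after-1-year estimate is unreliable for this reason. Two extra events in the smaller arm of the 4-against-15 illustration would give about 0.36 (0.14-0.93), and three about 0.42 (0.17-1.03). That requires every missed event to fall in one arm, for which the documents give no evidence. It shows how sparse the comparison is, not that it is biased.

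**Conclusion.** The point holds as a gap in the rules. SAP 2.5 and the protocol disagree on when the closing visit may take place, and SAP 2.8 does not clearly say where a patient seen before month 24 is censored. The literal reading credits event-free time that no scheduled contact covers.

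For the primary outcome the size is small: at most about 3% of expected procedures and 1 point of power. Bias in the overall hazard ratio would need visit timing or late event rates to differ by arm. The larger exposure is the mortality result, at up to 10% of expected deaths. Death is also the competing event in the primary analysis. How far missed late deaths matter there depends on the form of the model: in a subdistribution model a patient who has died stays in the risk set anyway. Absolute two-year risks and the after-1-year comparison are exposed too, the latter because it rests on few events.

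These sizes rest on the protocol's planning rates and on an unknown share of early visits. Severity: minor to moderate.

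**What to change.** 1. State the censoring date for a closing visit before month 24, and reconcile the SAP 2.5 window with Protocol 6.3, Figure 7 and Appendix 1.
2. Keep the 21-30 month window for functional and quality-of-life scores only.
3. For secondary procedures, hip-related complications and death, follow a patient to month 24 only if status is confirmed on or after month 24 by a visit, call or record already available. Otherwise censor at the date of last actual contact.
4. Apply that cut-off to events and non-events alike. If later events reported spontaneously are counted while event-free patients are censored early, risk is overstated.
5. Count patients without confirmed month-24 status as incomplete in sensitivity analysis (e), and report how many there are in each arm.

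**Cost.** The SAP is written in the past tense and describes analyses made after unblinding, so this means clarifying the rule and, if the literal rule was used, re-running the models. It should need only visit and contact dates that the trial already holds. The price is a slightly lower stated completeness of follow-up. A further record check at month 24 is optional where data collection is still open; it takes site time and should not be a condition of the fix.

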2.6 Outcome Definitions

Primary Outcome

| Outcome | Definition |
|---|---|
| Unplanned Secondary Hip Procedure (study event) | Unplanned secondary procedures that were classified as study events included: 
 ○ Closed reduction of hip dislocation ○ Open reduction of hip dislocation ○ Open reduction of fracture ○ Soft tissue procedure ○ Insertion of antibiotic spacer ○ Full implant exchange ○ Partial implant exchange – stem only ○ Partial implant exchange - head only ○ Partial implant exchange - liner only |

| Outcome | Definition |
|--|---|
| | 
 ○ Partial implant exchange - head and liner ○ Partial implant exchange – acetabular component only ○ Partial implant exchange – acetabular component and head ○ Implant adjustment – re-orientation of the stem ○ Implant adjustment – re-orientation of the acetabulum component ○ Implant removal with no replacement ○ Excision heterotopic ossification ○ Supplementary fixation ○ Other |
| Reason for Unplanned Secondary Procedure | 
Classification of the reason for unplanned secondary procedures included:
 
 ○ Treat a peri-prosthetic fracture ○ Treat hip instability or dislocation ○ Treat infection – superficial ○ Treat infection – deep ○ Treat wound necrosis ○ Treat another wound healing problem ○ Remove heterotopic ossification ○ Manage abductor failure ○ Manage another soft tissue problem (i.e. pseudotumor) ○ Correct implant failure –loosening or subsidence ○ Correct implant failure - breakage ○ Treat implant wear ○ Treat osteolysis ○ Treat implant corrosion ○ Improve function ○ Relieve pain |

Secondary Outcomes

| Outcome | Definition |
|--------------------------|---|
| Mortality | Mortality was adjudicated by the Central Adjudication Committee and it was considered to be an event if it occurred within 24-months of the initial hip fracture surgery. |
| Serious Adverse Events | Serious adverse events, as diagnosed by physicians at the clinical sites, were documented. A serious adverse event was defined as any adverse event that is fatal, life threatening, requires or prolongs hospital stay, results in persistent or significant disability or incapacity, a congenital anomaly or birth defect, or an important medical event, symptom, sign, illness, or experience that develops or worsens in severity during the study. |
| Hip-Related Complication | The Central Adjudication Committee reviewed hip-related complications including peri-prosthetic fracture, hip instability or dislocation, implant failure (loosening/subsidence and breakage), wound healing problems (including superficial/deep infection, wound necrosis), soft tissue problems (i.e. pseudotumor), heterotopic ossification, abductor failure, implant wear |

| Outcome | Definition |
|---|--|
| | and corrosion, osteolysis, neurovascular injury, decreased function, and pain. |
| Functional Outcomes and Quality of Life | 
Functional outcome and quality of life were measured using self-administered and interview-administered questionnaires. Functional outcome questionnaires included a generic health status measurement instrument (SF-12), a hip function and pain questionnaire (WOMAC), a health outcome measure (EQ-5D), and a functional mobility test (TUG).
 
The SF-12 Health Survey is a standardized instrument to measure health-related quality of life. This self-administered, 12-item questionnaire covers eight main health domains that make up the Physical and Mental Health Composite Scores (PCS & MCS). Each domain consists of one or two questions and is scored separately from 0 (lowest level) to 100 (highest level).
 
The WOMAC is a self-administered questionnaire that assesses the three dimensions of pain, disability and joint stiffness in knee and hip osteoarthritis, and consists of 24 questions. This questionnaire uses a Likert scale, consisting of responses including: none, mild, moderate, severe, and extreme. Specifically, for the WOMAC questionnaire, the Likert scale is in reverse order. Therefore, a higher score indicates worse pain, stiffness, and functional limitations. The ranges for each dimension are: 0-20 for pain, 0-8 for stiffness, and 0-68 for physical function.²
 
The EQ-5D is a standardized instrument that measures quality of life in five dimensions (mobility, self-care, usual activities, pain/discomfort, and anxiety/depression). Each dimension has three response options: 1=no problems, 2=some problems, and 3=extreme problems. Each response corresponds with a one-digit number that can then be combined into a 5-digit number to describe the participant's state of health. The participant's state of health is then translated into a corresponding utility score.² The EQ-5D also includes a visual analogue scale (VAS) that assesses the individual's health today on a scale from 0-100, with the endpoints being 'worst imaginable state of health' and 'best imaginable state of health'.^{3,4}
 
The TUG test is a standardized, physical test to assess balance and mobility in the participants. The participant is timed while they perform simple physical movements, such as rising from an arm chair, walking 10 feet, walking back to the chair, and sitting down. A faster time indicates that the participant has greater functional performance, while a lower score may identify participants who are at risk for increased falls in the community.⁵
 
The SF-12, WOMAC, and EQ-5D were asked at 10 weeks, 6, 9, 12, 18, and 24-month visits. The TUG was performed at 1 and 10-week 6, 12, and 24-month visits.
 |
